12.1.7. Publication

It is understood by the investigator that the sponsor shall be free to use the compound-related information, which is generated during the clinical study and may disclose it to other clinical investigators and to regulatory agencies. As a consequence, the investigator agrees to provide all clinical study results and data generated during this clinical study to the sponsor.

The investigator shall not be authorized to submit the results of this clinical study and any data for public disclosure (e.g. publication or presentation) without the prior written approval of the sponsor, which shall not be unreasonably withheld.

However, it is understood and agreed by the investigators that their results and/or findings shall not be authorized for publication prior to sponsor's publication of the overall clinical study results. The investigator agrees that prior to the publication of any results, he/she shall provide the sponsor with a draft copy of the intended publication. The sponsor shall have the right to review it and to make any comments. In accordance with generally accepted scientific collaboration principles, co-authorship with any staff member sponsor involved in the clinical study, will be discussed and mutually agreed upon before submission of any manuscript to a publisher.

12.2. Investigator's Responsibilities

12.2.1. Source Data and Data Capture

The nature and location of all source documents need to be identified and documented to ensure that all sources of original data required to complete the CRF are known and are accessible for verification by the monitor.

Source data may be directly captured from devices transferred from third partners (e.g. laboratory data) or entered manually into the CRF. The CRF completion guidelines will be provided to each investigational site.

It is recommended that the author of an entry in the source documents should be identifiable. Following ICH-GCP guidelines, direct access to sponsor's representatives to source documents must be granted for the purpose of verifying that the data recorded on the CRF are consistent with the original source data.

12.2.2. Archiving

Unless local legislation requires archiving for a longer period, the investigator shall archive the content of the clinical investigator site file (ISF) for at least 25 years after the end of the clinical study. However, the medical files of subjects shall be archived in accordance with national law.

The investigator should take measures to prevent accidental or premature destruction of these documents.

Under no circumstance shall the investigator relocate or dispose any clinical study documents before having obtained a written approval of the sponsor.

If it becomes necessary for the sponsor or the appropriate Regulatory Authority to review any documentation relating to this clinical study, the investigator must permit access to such reports. The subject is granting access to his/her source data by signing the ICF.

Any difficulty in storing original documents must be discussed with the monitor prior to the initiation of the clinical study.

12.2.3. Participation Cards

If the subjects are not under 24-hour supervision of the investigator or site staff, they must be provided with a subject participation card indicating the name of the IP, the clinical study number, the investigator's name, and the site's 24-hour emergency contact number. The subject should be advised to keep the participation card in his/her wallet at all times.

12.3. Confidentiality

The subject will receive all information as required by the EU General Data Protection Regulation, namely the identity and contact details of the controller, the contact details of the data protection officer, the clinical research purposes, the legal basis for the processing, the recipients

of the personal data, the transfer of the personal data to third countries and respective safeguards, the retention periods, the fair processing of his data, and all his/her data subject's rights. All details are listed in the ICF.

All information concerning the product and the sponsor's operations (such as patent applications, formulas, manufacturing processes, basic scientific data, or formulation information supplied to the investigator by the sponsor and not previously published) is considered confidential and should not be disclosed by the investigator to any third party without the sponsor's prior written approval. The investigator agrees to use this information only in accomplishing the clinical study and will not use it for other purposes.

In order to permit easy identification of the individual subject during and after the clinical study, the investigator is responsible for keeping an updated Subject Identification Code List. The monitor will review this document for completeness. However, the investigator must guarantee the subject's anonymity will be maintained. Therefore, in order to ensure subject confidentiality, the Subject Identification Code List must remain at the center and no copy will be made.

12.4. Ethical Considerations

12.4.1. Independent Ethics Committee / Institutional Review Board

This clinical study can only be undertaken after IEC/IRB approval of this CSP together with all relevant documentation. This approval document must be dated and clearly identify the clinical study and the related clinical study documents being approved, including the subject compensation programs, if applicable.

During the course of the clinical study, at least the following documents will be submitted to the IEC/IRB, per local requirements:

- Changes to the IB
- Reports of AEs that are serious, unlisted, and associated with the IP (in compliance with IEC/IRB, per local requirements)
- CSP amendments
- ICF amendments

After the subject has completed the study, the subject will receive a financial compensation, or depending on the country, the study physician may offer the option of a course of post-study medication approved for the treatment of RA, at no cost and for a duration of up to 6 months. Subjects will be eligible for compensation in case a subject received at least 1 dose of IP and completed the study, or discontinued early for e.g. safety reasons. In case a subject withdraws from the study early compensation will be pro rata, unless the reason for withdrawal from the study is noncompliance, then no compensation will be provided. Any form of compensation and conditions for compensation will require approval by an IEC and documented in the ICF.

The IEC/IRB is responsible for continuous review of the clinical study. Where required by IEC/IRB, per local requirements, at least once a year the investigator will provide the IEC/IRB

with a progress report to allow review of the clinical study. Additional progress reports should be provided according to local legal requirements. These requests and (re-)approvals, if applicable, should be documented in writing.

12.4.2. Informed Consent

The investigator or designated personnel must explain the clinical study and the implications of participation (e.g. objectives, methods, anticipated benefits, possible risks) to potential subjects according to applicable regulations prior to any clinical study-related activity. Subjects will be informed that their participation is voluntary and that they may withdraw from the clinical study at any time. They will be informed that choosing not to participate or to withdraw from the clinical study will not have an impact on the care the subject will receive for the treatment of his/her disease.

The subject will be given sufficient time to read the ICF and to ask additional questions. After this explanation and before entry in the clinical study, the subject's consent should be appropriately recorded by means of the subject's personally dated signature and by the investigator's dated signature. In case the subject is unable to read and/or write, oral consent in the presence of at least one impartial witness who was also included when the affected person was being informed, may be given. The witness may not be anyone working at the site nor a member of the investigating team. The orally given consent shall be documented in writing, dated and signed by the witness. After having obtained the consent, a copy of the signed and dated ICF must be given to the subject.

If new information becomes available relevant to the subject's willingness to participate in the clinical study, the subject will be informed in a timely manner by means of an amended ICF. This amended ICF will be signed and dated by the subject (or, if applicable, by an independent witness) and the investigator to document the willingness of the subject to continue with the clinical study.

This signed and dated amended version will be filed together with the initial signed and dated ICF.

A pregnant partner, who agrees that information will be gathered about her pregnancy and the birth, will be asked to sign a specific ICF to participate in the data collection. Data about the health of the baby will be collected if the parent(s)/legal guardian(s) agree with the data collection and sign a specific ICF.

Subjects who agree to participate in the study and who have signed informed consent, will be given the option to provide additional (and optional) informed consent for the long term storage of left over samples and associated data, collected during the study, for future scientific research.

12.5. Data Quality Control/Assurance

12.5.1. Monitoring

Data quality will be assured through Risk-Based Monitoring, medical monitoring, and other relevant activities as described in the Data Management Plan or Medical Review Plan and monitoring plans available in the TMF. This clinical study will be monitored by sponsor representatives according to their current standard operating procedures.

To guarantee adequate protection of the subjects and to guarantee the quality of the data, the sponsor will ensure oversight of any clinical study-related duties and functions carried out on its behalf, including clinical study-related duties and functions that are subcontracted to another party by the sponsor's contracted CRO(s).

A risk-based Quality Management Plan (QMP) is prepared for the study that evaluates potential risks in relation to rights, safety, and well-being of the study subjects as well as the data integrity. The QMP describes and evaluates all involved stakeholder interfaces having potential critical impact on the above. Risks are considered at both the system level (e.g. standard operating procedures, computerized systems, personnel, and vendors) and study level (e.g. IP, study design, data collection, informed consent process and recording).

12.5.2. Audit and Inspection

To ensure compliance with relevant regulations, an independent quality assurance representative, regulatory authorities and/or IECs/IRBs may review this clinical study. This implies that auditorsinspectors will have the right to inspect the clinical study center(s) at any time during and/or after completion of the clinical study and will have access to the data generated during the clinical study, source documents, and subject's files. By participating in this clinical study, investigators agree to this requirement.

14. APPENDICES

Appendix 7: Prednisolone Conversion Table

Glucocorticoid Name	Dose Equivalent to 5 mg Prednisolone
Prednisone	5 mg
Betamethasone	0.6 mg
Cortisol (hydrocortisone)	20 mg
Cortisone	25 mg
Deflazacort	7.5 mg
Dexamethasone	0.75 mg
Methylprednisolone	4 mg
Methylprednisolone Acetate	4 mg
Methylprednisolone Sodium Succinate	4 mg
Paramethasone	2 mg
Prednisolone	5 mg
Triamcinolone	4 mg
Beclometasone Dipropionate	1.25 mg
Budesonide	1.5 mg
Hydrocortisone Sodium Succinate	20 mg

(Steriod Conversion Calculator)

Appendix 8: Algorithm for Elevated Liver Function Tests

	AST or ALT increase to				
Value Range	$\geq 1.5x$ to $3x$ ULN	$\geq 3x$ to $<5x$ ULN	$\geq 5x$ to $<8x$ ULN	$\geq 3x$ ULN with signs of liver damage ¹	$\geq 8x$ ULN
IP Action	Continue as planned	Reduce or interrupt IP for at least 2 weeks	Interrupt IP for at least 2 weeks Close observation ²	Discontinue IP ²	Discontinue IP ²
		Close observation ²			
After at least 2 weeks	AST and ALT $<3x$ ULN	AST or ALT $\geq 3x$ ULN			
	Weekly LFTs for the first 2 weeks (biweekly for the following weeks, or more frequently at investigator's discretion)	Discontinue IP Report SAE and complete liver event page for any of abnormalities listed below ³ : 
 - AST/ALT increase $\geq 8x$ULN - AST/ALT increase $\geq 3x$ULN with signs of liver damage¹ 			

¹ Signs of liver damage:

- total bilirubin $\geq 2.0x$ ULN OR international normalized ratio >1.5 , and/or
- symptoms: appearance of fatigue, nausea, vomiting, right upper abdominal quadrant pain or tenderness, fever, rash and/or eosinophilia ($>5\%$)

² Close observation recommendations:

- Monitor 2 to 3 times per week all of the following parameters: ALT, AST, ALP, total bilirubin, eosinophils, INR. If local regulations allow, home visits can be performed if subjects cannot come to the clinical study center.
- Frequency of retesting can be reduced to once a week or less if abnormalities stabilize or the IP has been discontinued; however, monitoring might still be needed more frequently taking into consideration the standard of care and/or changes to this.
- Based upon investigator's discretion gastroenterology or hepatology consultations, additional serology testing, imaging, and pathology assessments may be required.
- Re-query history of symptoms, prior and concurrent diseases, concomitant medication and non-prescription medicines, herbal, dietary supplements, alcohol use, recreational drug use, special diets.
- Rule out all of the following: acute viral hepatitis, autoimmune hepatitis, alcoholic hepatitis, non-alcoholic fatty hepatitis, hypoxic/ischemic hepatitis, biliary tract disease, and cholestasis.
- Re-query exposure to environmental chemical agents.

³ The following steps should be followed:

- The site should immediately contact the subject and require the subject to discontinue IP immediately. The subject should be asked to return to the site within a 48-hour window from awareness of the result.
- A full evaluation of various causes of hepatitis should be conducted (i.e. infectious, alcohol, medications, anatomical).

- An assessment of other concomitant medications and standard of care should be made. The investigator should consider to whether is in the best interest of the subject to stop/interrupt concomitant medications and SOC treatment.
- A detailed history including relevant information on alcohol use, recreational drug use, supplement consumption, any herbal remedies, family history, sexual history, travel history, history of contact with a jaundiced subject, surgery, occupational history, blood transfusion, history of liver or allergic disease, and any other potential causes of attributable to a liver insult should be collected.
- A detailed assessment of the subject's clinical condition and repeat laboratory tests for LFT, including albumin, creatine kinase, total bilirubin (direct and indirect), GGT, INR, and ALP should be done.
- Further testing for Hepatitis A, B, and C, and for autoimmune hepatitis should be done. Other causes of viral hepatitis (cytomegalovirus or Epstein-Barr virus etc) should be excluded. Liver imaging should be considered.
- Referral to a hepatologist or gastroenterologist should be requested.
- All these cases should be reported as SAEs.

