5.5. Potential Risks and Benefits

GLPG3970 has been studied in a nonclinical setting (Section 2.1) and is being studied in a FIH study (Section 2.2) where the single and multiple ascending dose parts of the study are completed up to the dose of 400 mg q.d. GLPG3970 was well tolerated at all dose levels studied in the FIH study. Study GLPG3970-CL-209 is the first study where GLPG3970 is being administered to subjects with RA.

GLPG3970 has a novel dual mechanism of action, which is intended to restore the balance of the immune system by reducing several mediators of inflammation and by improving immune-regulatory mechanisms that may be impaired in autoimmune diseases such as, for example, RA, psoriasis, and inflammatory bowel disease. Thus, this may weaken the immune response and can potentially increase subject's risk to developing infections (opportunistic infections, SARS-CoV-2, etc). Careful monitoring and reporting of signs and symptoms is therefore required, to enable prompt medical evaluation and pharmacological or clinical intervention.

Based on the mechanism of action of GLPG3970 and its potential to control pro-inflammatory and immunomodulating cytokines, such as TNF α and IL-10, an improvement of clinical symptoms of RA may be derived.

Risk Mitigation

Mitigation measures have been taken to ensure safety of the subjects targeting population selection, dose, concomitant medications, and safety surveillance on certain laboratory parameters and biomarkers. Information on important safety risks is included in the latest version of the IB.

In the forthcoming study subjects' risk will be minimized by implementing conservative eligibility criteria, including RT-PCR testing to exclude subjects with SARS-CoV-2, by standard laboratory tests, by collecting TEAEs throughout the study, and monitoring of subjects for infection symptoms. Any potential negative effects of GLPG3970 will be carefully assessed through regular physical assessments and laboratory monitoring that will happen at every visit. Laboratory alerts will be set up for the study in order to early inform the study investigator and the sponsor on highly abnormal laboratory values (severity Grade 3 and above). A Data Safety Monitoring Committee will monitor unblinded data.

- [REDACTED]

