6.3.3. Food and Beverage Restrictions

Subjects must come for the study visits, during the treatment and FU period, in the morning. At Visit 1, 3, 5, and if applicable the ED visit, subjects need to come for the study visits in a fasting state (no food intake for at least 8 hours).

Subjects will refrain from the consumption of grapefruit juice, grapefruit or Seville oranges beginning 48 hours prior to administration of the initial dose of IP, throughout the study until 7 days after the last IP administration.

6.4. Treatment Discontinuation (Temporarily and Permanently), Subject Withdrawal and Study Termination

A subject may be withdrawn from the clinical study at any time without the subject's consent if the investigator or sponsor determines that it is not in the best interest of the subject to continue participation. In such case, the reason for withdrawal will be documented in the source

documents, and the subject will be asked to complete the ED visit and FU visit for safety assessments.

Treatment with IP should be discontinued by the investigator (who may consult the sponsor's medical responsible) for any of the following conditions:

- Life-threatening adverse event (AE) or a serious adverse event (SAE) that places the subject at immediate risk.
- Serious infections deemed related to study treatment by the investigator, and requiring parenteral antimicrobial therapy and/or hospitalization.
- Confirmed pregnancy or lactation.
- Arrhythmia or conduction abnormality, including but not limited to prolonged QT interval corrected for the heart rate using Fridericia's formula (QTcF), where the severity is categorized as Common Terminology Criteria for Adverse Events (CTCAE) Grade 3 or higher (QTcF >500 ms on at least 2 separate ECGs) or clinically significant arrhythmia of any grade.
- Liver enzyme increase (see also [Appendix 8](#))
 - AST and/or ALT ≥ 8 x the ULN.
 - AST and/or ALT elevations ≥ 3 x ULN with signs of liver damage (i.e. with the appearance of fatigue, nausea, vomiting, right upper quadrant pain or tenderness, fever, rash and/or eosinophilia [$>5\%$], and/or total bilirubin ≥ 2.0 x ULN or international normalized ration [INR] >1.5)
 - In addition, a dose interruption or reduction (if applicable) should be considered if AST and/or ALT ≥ 3 x ULN and <5 x ULN and dosing with IP should be interrupted if AST and/or ALT ≥ 5 and <8 x ULN.

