11.1.4. Adverse Events of Special Interest

Not applicable.

11.1.5. Clinical Laboratory Abnormalities and Other Abnormal Assessments as Adverse Events or Serious Adverse Events

Laboratory abnormalities without clinical significance based on the investigator's judgment are not considered AEs or SAEs. However, laboratory abnormalities (e.g. clinical chemistry, hematology, and urinalysis) or other abnormal (clinical study-specific) assessments (e.g. ECG, radiography, vital signs) that require medical or surgical intervention, are associated with signs and/or symptoms, and/or lead to IP interruption, modification or discontinuation must be recorded as an AE or SAE if they meet the definition as described in Sections 11.1.1 and 11.1.2, respectively. If the laboratory abnormality is part of a syndrome, the syndrome or diagnosis is to be reported (e.g. anemia instead of decreased hemoglobin).

The following liver enzyme elevations should be reported as SAEs:

- AST or ALT ≥ 8 xULN.
- AST or ALT ≥ 3 xULN with signs of liver damage (total bilirubin >2 xULN OR international normalized ratio >1.5 , and/or with the appearance of fatigue, nausea, vomiting, right upper quadrant pain or tenderness, fever, rash and/or eosinophilia [$>5\%$]).

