APPENDIX

APPENDIX I: LABORATORY: TOXICITY GRADING

The following tables contain a list of safety tests with associated gradings. There may be tests in this table that are not measured in this particular study.

Table 1 Gradings for Hematology Parameters

Parameter	L1	L2	L3	L4	H1	H2	H3	H4
Hemoglobin	<LLN	<10 g/dL; <6.2 mmol/L	<8 g/dL; <4.9 mmol/L	NA	>ULN	Increase in >2 g/dL above ULN	Increase in >4 g/dL above ULN	NA
Hematocrit	<LLN	NA	NA	NA	>ULN	NA	NA	NA
Mean corpuscular volume (MCV), mean corpuscular hemoglobin (MCH), mean corpuscular hemoglobin concentration (MCHC)	<LLN	NA	NA	NA	>ULN	NA	NA	NA
Platelet count - (assuming no platelet cluster)	<LLN	<75 x 10 ⁹ /L	<50 x 10 ⁹ /L	<25 x 10 ⁹ / L	>ULN	>600 x 10 ⁹ /L	>1000 x 10 ⁹ /L	NA

Parameter	L1	L2	L3	L4	H1	H2	H3	H4
Leukocytes	<LLN	<3.0 x 10 ⁹ /L	<2.0 x 10 ⁹ /L	<1.0 x 10 ⁹ /L	>ULN	>20.0 x 10 ⁹ /L	>100.0 x 10 ⁹ /L	NA
% Polymorphonuclear Leukocytes + Band Cells	NA	NA	NA	NA	>ULN	≥90%	>95%	NA
Neutrophils	<LLN	<1.5 x 10 ⁹ /L	<1.0 x 10 ⁹ /L	<0.5 x 10 ⁹ /L	NA	NA	NA	NA
Eosinophils	NA	NA	NA	NA	>ULN	>5.0 x 10 ⁹ or eosinophils >5%	NA	NA
Lymphocytes	<LLN	<0.8 x 10 ⁹ /L	<0.5 x 10 ⁹ /L	<0.2 x 10 ⁹ /L	>ULN	>4.0 x 10 ⁹ /L	>20.0 x 10 ⁹ /L	NA

Parameter	L1	L2	L3	L4	H1	H2	H3	H4
Red blood cells	<LLN	NA	NA	NA	>ULN	NA	NA	NA

Table 3 Gradings for Blood Chemistry Parameters

Parameter	L1	L2	L3	L4	H1	H2	H3	H4
Alanine aminotransferase (ALT)	NA	NA	NA	NA	>ULN	>3.0 x ULN	>5.0 x ULN	>8.0 x ULN
Aspartate aminotransferase (AST)	NA	NA	NA	NA	>ULN	>3.0 x ULN	>5.0 x ULN	>8.0 x ULN
Gamma-glutamyl transferase (GGT)	NA	NA	NA	NA	>ULN	>2.5 x ULN	>5.0 x ULN	>20.0 x ULN
Alkaline Phosphatase (total)	NA	NA	NA	NA	>ULN	>2.5 x ULN	>5.0 x ULN	>20.0 x ULN
Lactate dehydrogenase (LDH)	NA	NA	NA	NA	>ULN	NA	NA	NA
Total bilirubin	NA	NA	NA	NA	>ULN	>1.5 x ULN	>3.0 x ULN	>10.0 x ULN
Amylase	NA	NA	NA	NA	>ULN	>1.5 x ULN	>2.0 x ULN	>5.0 x ULN
Lipase	NA	NA	NA	NA	>ULN	>1.5 x ULN	>2.0 x ULN	>5.0 x ULN
Total protein	<LLN	<5.5 g/dL	<5.0 g/dL	NA	NA	NA	NA	NA
Activated partial thromboplastin time (APTT)	NA	NA	NA	NA	>ULN	>1.5 x ULN	>2.5 x ULN	NA

Parameter	L1	L2	L3	L4	H1	H2	H3	H4
Prothrombin time (PT)	NA	NA	NA	NA	≥1.10 x ULN	≥1.25 x ULN	≥1.50 x ULN	≥3.00 x ULN
International normalized ratio (INR)	NA	NA	NA	NA	>1.2 x Baseline	>1.5 x Baseline	>2.5 x Baseline	NA
Creatinine	NA	NA	NA	NA	>ULN	>1.5 x ULN	>3.0 x ULN	>6.0 x ULN

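### For AST/ALT of 3 to under 5 times ULN, Protocol Section 6.4 makes holding the drug optional, while Appendix 8 directs a hold and adds a stop for persistent elevation

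*Protocol*

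**What the plan says.** Protocol Section 6.4 lists the conditions for stopping IP. Under liver enzyme increase, the stops are AST or ALT at 8 times ULN or more, or at 3 times ULN or more with signs of liver damage. For 3 to under 5 times ULN it says "a dose interruption or reduction (if applicable) should be considered if AST and/or ALT" fall in that range. For 5 to under 8 times ULN the same sentence says dosing should be interrupted. The item carries a pointer to Appendix 8.

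Appendix 8 keeps uninterrupted dosing for the band below 3 times ULN. For 3 to under 5 times ULN its IP action is "Reduce or interrupt IP for at least 2 weeks", with close observation. If AST or ALT is still at or above 3 times ULN after at least 2 weeks, the entry begins "Discontinue IP Report SAE and complete liver event page". The SAE report there applies only at 8 times ULN or more, or at 3 times or more with signs of liver damage. Close observation is described as "Monitor 2 to 3 times per week all of the following parameters: ALT, AST, ALP, total bilirubin, eosinophils, INR", under a label that calls these items recommendations.

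Section 11.1.5 says that laboratory abnormalities that "lead to IP interruption, modification or discontinuation must be recorded as an AE or SAE", provided they meet the AE or SAE definition. By contrast, "Laboratory abnormalities without clinical significance" in the investigator's judgment are not AEs.

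**The concern.** The same laboratory value leads to different dosing depending on which page a site follows. Section 6.4 is where an investigator would look for stopping conditions, and the persistence stop is missing from it. This is the first study of the drug in rheumatoid arthritis, and every subject also takes methotrexate.

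There may also be no automatic check on a site that continues dosing. Section 5.5 sets laboratory alerts for "highly abnormal laboratory values (severity Grade 3 and above"). SAP Appendix I grades AST and ALT above 3 times ULN as grade 2 and above 5 times as grade 3. If the alert uses those cutoffs, which the protocol does not state, this band would not trigger it.

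**Working it through.** The plan states no figure on this point to reproduce. The check compares the two texts and then works out the scale for one affected subject.

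**The texts for 3 to under 5 times ULN, no signs of liver damage**

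| Element | Section 6.4 | Appendix 8 |
|---|---|---|
| IP action | Consider interruption or reduction | Reduce or interrupt |
| Minimum duration | None given | 2 weeks |
| Extra monitoring | Silent | Close observation, 2 to 3 times a week |
| Still at least 3 times ULN after at least 2 weeks | Nothing stated | Discontinue |
| Which text governs | Points to Appendix 8 only | Not stated |

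The Appendix 8 table was flattened in extraction. The persistence row is read in its natural order.

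1. *Is Section 6.4 discretionary?* Yes. One sentence uses permissive wording for this band and directive wording for the next, so the contrast looks deliberate.
2. *Does the word reduce reconcile them?* No. Section 5.1 has one dose level, Section 7.2 requires the whole solution to be drunk, and the action-taken options in Section 11.2.3 include no reduction. Interruption is the only Appendix 8 action a site can carry out.
3. *Is monitoring contradictory?* No. Section 6.4 omits it for this band.

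**Scale per subject.** The inputs are on-treatment safety bloods after Day 1 on Days 15, 29 and 43 (Section 8.11), 400 mg once daily, and 6 weeks = 42 days of dosing.

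- Gap between samples: 29 − 15 = 14 days.
- Dosing continued on Days 16 to 29: 14 × 400 mg = 5,600 mg. Under an Appendix 8 interruption: 0 mg, ignoring laboratory turnaround.
- Panels added between visits: 2 to 3 per week × 2 weeks = 4 to 6 if the recommendations are followed throughout. Section 6.4 requires none.
- Minimum interruption: 14/42 = 33% of planned dosing.

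**Timing of the persistence stop.** A Day 15 trigger gives a recheck at 15 + 14 = Day 29, which leaves two weeks in which the subject is either discontinued or still dosed. A Day 29 trigger gives 29 + 14 = Day 43, which is already the Week 6 visit. Among scheduled bloods, essentially only a Day 15 elevation persisting to Day 29 can change treatment-discontinuation status before Week 6.

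**TEAE incidence.** One subject is 1/15 = 6.7 points on GLPG3970 or 1/10 = 10 points on placebo. That shift occurs only if the event meets the AE definition, is recorded under one text and not the other, and is the subject's only TEAE.

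**Frequency.** None is documented. Assuming a per-subject risk p of entering the band, the chance of at least one case among 25 is 1 − (1 − p)^25: 40% at p = 2%, 72% at 5%, 93% at 10%. This says nothing about how often a site would also follow Section 6.4 alone.

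**The case against.** The best defence is the cross-reference. The liver item in Section 6.4 sends the site to Appendix 8, a site that follows Appendix 8 also complies with Section 6.4, and every adverse consequence needs a site to stop reading at Section 6.4. This stands in part: a careful site will probably reach the stricter rule. It does not remove the conflict, because the pointer gives no precedence, and considering a hold is not the same rule as holding for at least two weeks.

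A reader might infer that a subject kept on drug would go two weeks without liver tests. The documents do not support that. Sections 8.2 and 8.5 allow unscheduled visits and extra laboratory tests, Section 8.5.2 has the investigator assess out-of-range values, and Section 10.1 provides a committee reviewing unblinded safety data. Close observation in Appendix 8 is also a recommendation that can be relaxed if values stabilise, so 14 doses with no tests against none with 4 to 6 panels compares two extremes.

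A reader might also infer that the TEAE endpoint or the primary estimand is compromised. That goes too far as well. Interruption triggers AE recording only when the AE definition is met, and symptoms or a need for intervention trigger it too. A temporary interruption is not early treatment discontinuation, so the hypothetical strategy in SAP Section 3 would apply differently only after a persistence stop. SAP Section 6.3.2.8 tabulates AST and ALT above 3 times ULN whichever text was followed, so the laboratory signal is kept.

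**Conclusion.** The inconsistency is real. For one enzyme band the protocol gives a discretionary rule in Section 6.4 and a directed hold with a persistence stop in Appendix 8, and it does not say which governs. The consequence is mainly for subject safety and uniform conduct across sites: up to 14 doses that one text permits and the other withholds.

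Effects on the secondary TEAE endpoint and on the primary estimand are possible but indirect, and no size can be given for either because the documents contain no frequency for this band. The conclusion rests on reading the persistence row of Appendix 8 as applying to this band. It does not depend on the alert cutoffs or the assumed risks. This merits an amendment but does not threaten the trial's analysis.

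**What to change.** Amend Section 6.4 to state the Appendix 8 rule for AST or ALT from 3 to under 5 times ULN: interrupt IP for at least 2 weeks, with close observation per Appendix 8. Add to the Section 6.4 discontinuation conditions that IP is stopped if AST or ALT is still at or above 3 times ULN after that time. Delete the reduction option in both places, since no lower dose exists.

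The edit is about one sentence in Section 6.4 and two words in Appendix 8, made by protocol amendment with notice to sites. It needs no new visits, kits or CRF fields.

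The downside is that investigators lose discretion over modest rises that may come from methotrexate. Each case loses at least 14 of 42 treatment days, and a Day 29 case will be off drug at Week 6. If the sponsor wants to keep that discretion, the permissive wording should go into Appendix 8 instead and close observation should be made a requirement. Either way sites would have one rule.
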